2 STUDY RATIONALE

PCa is the most prevalent cancer in men in the developed world and the third leading cause of death ([Jemal 2011](#)). It is most commonly diagnosed in men aged 65 years and over and

diagnosis is often made following the detection of elevated PSA and/or an abnormal digital rectal examination, with confirmation of this diagnosis by prostate biopsy. PSA is used as a tumor marker and serum levels of PSA positively correlated with the risk of metastatic disease or subsequent disease recurrence or progression.

The PSMA receptor is a 100 kD transmembrane glycoprotein that is over-expressed in the majority of PCa ([Israeli 1994](#); [Silver 1997](#); [Osborne 2013](#)). Peptidomimetic glu-ureido-based PSMA inhibitors, initially described in 2001 ([Kozikowski 2001](#)), bind to a carboxypeptidase active site on the extracellular motif of the PSMA receptor. In the last 5 years, many centers around the world have imaged patients using PSMA PET tracers based on this targeting technology ([Perera 2016](#)). Whilst these initial results have demonstrated promising diagnostic performance, there remains no licensed or approved PSMA PET imaging agent.

rhPSMA-7.3 (¹⁸F) injection, is a PET ligand for the detection of PCa. The rhPSMA-7.3 (¹⁸F) stereoisomer has already been administered to patients at the TUM ([see Section 1.2](#)). Several hundred patients with PCa have been imaged clinically, which has informed the design of this proposed study. rhPSMA-7.3 (¹⁸F) is currently being formally evaluated by Blue Earth Diagnostics in a Phase 1, open label, study designed to assess the safety, biodistribution and internal radiation dosimetry of rhPSMA-7.3 (¹⁸F) injection in healthy volunteers, and to assess safety and investigate the imaging characteristics in patients with PCa (Study BED-PSMA-101; EudraCT No. 2018-004703-39).

As described in [Section 1.2](#), the detection rate of rhPSMA-7.3 (¹⁸F) varies depending on the PSA level at scanning. The findings at TUM are consistent with the recently published paper ([Fendler 2019](#)), describing the use of gallium-68 (⁶⁸Ga)-PSMA-11 in 635 patients with BCR irrespective of the results of other imaging. They reported an overall detection rate of 75%, but stratifying for PSA levels, the detection rates were 45%, 84%, 86%, and 97% for patients with PSA levels of <1 ng/mL, 1 to <2 ng/mL, 2 to <5 ng/mL and ≥5 ng/mL, respectively.

One of the major disadvantages of the (mostly retrospective) studies to date is the lack of confirmation of the finding on the PSMA PET scan. Although the detection rates (defined as the number of positive scans/all included patients) are reported, it is not known if every positive scan is a True Positive (TP) scan. Ideally, both the positive predictive value (PPV) and the *Correct Detection Rate* (CDR) of PET findings should be known. The CDR is defined as the percentage of all patients scanned who have at least one **TP** lesion (localized correspondence between rhPSMA-7.3 (¹⁸F) PET imaging and the reference standard) regardless of any coexisting False Positive (FP) findings. Unfortunately, in the [Fendler \(2019\)](#) study, confirmation of the positive scans was only obtained in 217 out of 635 patients. Therefore, the PPV and CDR cannot be determined for the entire study population.

Based on data from the retrospective chart review, data from the [Fendler \(2019\)](#) study, and from a comprehensive review of the literature, the influence of the PSA level at the time of scanning on detection rate and diagnostic performance cannot be underestimated.

In studies in patients with a PSA level ≥1 ng/mL, detection rates can range from 64% to over 90% ([Perera 2019](#)), with an average of 85%. In this multi-center US study of rhPSMA-7.3 (¹⁸F) (without the selection bias of many of the studies referenced by [Perera \[2019\]](#)), an estimated overall detection rate of ≥75% is reasonable for patients with a PSA level ≥1 ng/mL. [Fendler \(2019\)](#) reported PPVs of 92% (composite Standard of Truth [SoT]) and 84% (histopathologic SoT) in patients with median PSA levels of 3.5 and 3.9 ng/mL, respectively. It is expected, with a composite SoT including both histopathology (when available) and ¹⁸F-fluciclovine PET imaging (in cases without histopathology) to achieve a PPV of approximately 80% in this subpopulation.

However, in patients with a PSA level >0.2 to <1 ng/mL, PSMA scans can show detection rates between 46% and 63% ([Perera 2019](#)), with an average of 56%. A detection rate of 57% was reported by [Fendler \(2019\)](#) in patients with a PSA level of 0.5 to <1 ng/mL; this fell to 38% for patients with a PSA level <0.5 ng/mL. Therefore, an estimated overall detection rate of $\geq 45\%$ is reasonable for patients with a PSA level >0.2 to <1 ng/mL. Confirming that lesions seen on PSMA PET imaging are TP will be challenging in this subgroup, since these lesions may be small, prone to biopsy error, and not yet visible on other diagnostic imaging techniques. In patients with PSA levels <1 ng/mL and histopathologic data, the PPV is likely to be well below the 92% reported by [Fendler \(2019\)](#) for a group of patients with a median PSA level of 3.9 ng/mL. Additionally, no patients in this subgroup will have an intact prostate amenable to biopsy and we might expect only $\sim 50\%$ concordance between one example imaging reference standard test - ^{18}F -fluciclovine - and PSMA PET-positive patients ([Calais 2019](#)). Therefore, the PPV (using histopathology or conventional/confirmatory imaging as the SoT) is expected to be low, at approximately 65%. It is important to note that PSMA PET may be a more sensitive way of demonstrating disease in men with recurrent PCa, as compared to conventional imaging-based SoT ([Perera 2016](#)). Importantly, the overall PPV will also likely be decreased by patients with multiple PSMA PET-positive regions given histological confirmation of multiple lesions in the same patient is highly unlikely.

Most trials investigating diagnostic PSMA ligands have thus far focused on those patients with prior negative conventional imaging. Going forward in routine clinical care, given the low sensitivities of these conventional imaging procedures, it is difficult to continue to support subjecting patients to two or three non-sensitive imaging procedures before the patient may receive a more sensitive one. Based on the retrospectively determined high sensitivity of PSMA ligands ([Afshar-Oromieh 2015](#); [Eiber 2015](#); [Afshar-Oromieh 2017](#)), this study is designed to establish the performance of rhPSMA-7.3 (^{18}F) PET irrespective of the findings of conventional imaging in order to support the use of rhPSMA-7.3 (^{18}F) as an imaging option during the initial workup of these patients. This study will do so acknowledging the limitations of obtaining proof of true-positivity of the PSMA-positive lesions given the difficulties of obtaining histopathology in all patients and the relative insensitivity of other imaging modalities. Therefore, CDR and PPV are set at reasonable threshold levels, accounting for the limitations of the SoT and considering the significant influence of the PSA level on the scan's performance.

2.1 Risk-benefit Assessment

2.1.1 Benefits

The rhPSMA-7.3 (^{18}F) PET scans may provide further clinical information regarding the patient's disease status that may not have been appreciated by routine clinical testing. If such information arises, this will be reported back to the responsible clinician to help direct the patient's further management. This may provide a direct benefit to the patient.

In the current study, the maximum effective dose due to the CT transmission scan on a PET/CT scanner will vary from site-to-site, but as a guide a dose of 7 mSv would be expected. The effective dose due to the CT acquisition will be in accordance with ALARA (**As Low As Reasonably Achievable**) principles. The estimated total dose of 12 mSv (PET and CT transmission scan) is in line with other common nuclear medicine procedures.

If rhPSMA-7.3 (¹⁸F) PET shows one or more sites of recurrence and if clinically feasible, the most accessible lesions(s) will be biopsied under radiological guidance.

A CT-guided biopsy may be required in these patients; mean effective doses of between 4.3 to 13.9 mSv have been reported ([Guberina, 2018](#)) during CT-guided biopsies and is dependent on the organ region and CT-scanner generation. A biopsy will cause discomfort and pain and may incidentally lead to complications, like prolonged bleeding at the site of the biopsy or infection.

Confirmatory imaging may include the use of diagnostic CT or PET (see [Section 9.1.6](#)). Examples of effective doses from such procedures are as follows: abdominal/pelvic CT 6 to 8 mSv ([McCollough, 2015](#)); chest CT 7 mSv ([McCollough, 2015](#)); ¹⁸F-sodium fluoride (NaF) PET 8.9 mSv ([Beheshti, 2015](#)); Axumin (¹⁸F-Fluciclovine) PET 8 mSv (Axumin USPI; Axumin SmPC).

As with all imaging techniques there is the risk that the PET scan may provide a FP image (giving the appearance of cancer) in sites where it is not present, due to other events in the body or False Negative (failing to detect a nidus of cancer). Thus, patients should continue to be reviewed and may require other investigations, to confirm scan findings.

As described in [Section 1.2](#), as of 15 February 2019, rhPSMA-7.3 (¹⁸F) has been administered at TUM, under the physician's personal responsibility, to a total of 558 men with known or suspected PCa, including 285 patients with BCR of PCa after radical prostatectomy (RP) and radiation therapy (RT)/brachytherapy. Although 35 out of 146 patients with documents in their electronic medical records within 30 days after rhPSMA-7.3 (¹⁸F) injection had AEs or SAEs, there were no reports of adverse reactions or serious adverse reactions attributed to injection of rhPSMA-7.3 (¹⁸F) ([Study BED-PSMA-403](#)).

3 STUDY OBJECTIVES

3.1 Primary Objective

The primary objective of the study is to assess the patient level CDR and region level PPV of rhPSMA-7.3 (¹⁸F) PET for BCR of PCa using histopathology or imaging as a SoT. The CDR is defined as the percentage of all patients scanned who have at least one TP lesion (localized correspondence between rhPSMA-7.3 (¹⁸F) PET imaging and the reference standard) regardless of any coexisting FP findings. When determining the region level PPV, all rhPSMA-7.3 (¹⁸F) PET-positive regions will be categorized as TP or FP regions using histopathology or imaging.

3.2 Secondary Objectives

The secondary objectives of the study are to:

1. Assess the patient level CDR and region level PPV of rhPSMA-7.3 (¹⁸F) PET in the subgroup of patients who have negative baseline conventional imaging.
2. Assess the patient level CDR and region level PPV of rhPSMA-7.3 (¹⁸F) PET separated into subgroups of patients with reference standard histopathology available and unavailable.
3. Assess the patient level CDR and region level PPV of rhPSMA-7.3 (¹⁸F) PET stratified by PSA level.
4. Assess the CDR of rhPSMA-7.3 (¹⁸F) PET on a region level.
5. Assess the impact of rhPSMA-7.3 (¹⁸F) results on the intended clinical management of study participants using a clinician survey.
6. Assess the inter- and intra-reader agreement of rhPSMA-7.3 (¹⁸F) scan interpretation by the blinded independent readers.
7. Assess the safety of rhPSMA-7.3 (¹⁸F) injection in patients.

3.3 Exploratory Objectives

The exploratory objectives of the study are to:

1. Assess the overall detection rate (without SoT confirmation) on a patient level and including detection rate subgroup analyses of patients: a) who have negative baseline conventional imaging, b) with reference standard histopathology available and unavailable, and also detection rate stratified by PSA level and assessed by region.
2. Assess the patient level PPV in which a TP patient is defined as having at least one TP region, regardless of any coexisting FP regions.
3. Assess the impact of rhPSMA-7.3 (¹⁸F) PET on upstaging patients with BCR of PCa a) post-RP or b) post-RT compared to conventional imaging.
4. Assess patient and regional level detection rates of rhPSMA-7.3 (¹⁸F) PET.
5. Assess patient and regional level detection rates of rhPSMA-7.3 (¹⁸F) PET as a function of PSA, prior Gleason score, and PSA doubling time (PSAdt) in a) post-RP or b) post-RT patients.

4 STUDY DESIGN

4.1 Study Overview

This is a prospective, Phase 3, multi-center, single-arm, diagnostic imaging study designed to evaluate the safety and diagnostic performance of rhPSMA-7.3 (¹⁸F) PET ligand for imaging in men with suspected BCR of PCa based on elevated PSA following prior therapy.

Given the different performance of PSMA ligands in patients with PSA levels <1 ng/mL versus ≥ 1 ng/mL, the patient population will be weighted to prevent overrepresentation of patients with a PSA <1 ng/mL. The proportion of patients with a PSA <1 ng/mL will be maximized at approximately 40%, consistent with the study population studied by [Fendler \(2019\)](#). Once 60% of the planned 190 positive cases have information, the proportion of patients with a PSA <1 ng/mL will be assessed. If this proportion exceeds 60% then investigators will be informed to stop further enrolment of this cohort (see [Section 16.7](#)).

Patients with a diagnosis of BCR of PCa being worked up for re-staging and eligible for potential salvage treatment will be consented and enrolled. Patients will be screened at Visit 1 to determine eligibility for the study up to 28 days (up to 45 days due to the Corona Virus Disease-19 [COVID-19] pandemic) before rhPSMA-7.3 (¹⁸F) PET imaging at Visit 2. Patients who meet all of the inclusion criteria and none of the exclusion criteria will be assigned a patient identifier (ID) and entered into the study at screening. Participation in this study does not replace conventional imaging required for staging as per local guidelines/standard of care. If not already completed within 90 days before Visit 1, standard of care conventional imaging will be performed following Visit 1 and up to 2 weeks after Visit 2 (Optional Visit 2(a)). Conventional imaging that has been performed at non-participating institutions will be accepted provided the scans are reviewed by the participating institution. Patients will be asked to provide historical imaging if available and if performed as part of their PCa care and follow-up. After enrollment (either before or after conventional imaging if not already completed), patients will receive an administered activity of 8 mCi (296 MBq) \pm 20% rhPSMA-7.3 (¹⁸F), delivered as an IV bolus injection with a 10 mL fast 0.9% sodium chloride flush, followed by PET imaging.

Note: Due to the COVID-19 pandemic, the screening/eligibility evaluation may take place on the day of rhPSMA-7.3 (¹⁸F) administration (with pre-screening via telephone), if necessary, to ensure the safety of enrolled patients (see Visit 1 and Visit 2 combined; [Section 10.3](#)). Alternatively, the time from Visit 1 (initial screening) to Visit 2 (rhPSMA-7.3 (¹⁸F) PET scan) may be extended up to 45 days due to the COVID-19 pandemic.

If feasible, the patient will undergo image-guided biopsy of a PET-positive lesion(s) suspicious for recurrence of PCa within 45 days following rhPSMA-7.3 (¹⁸F) PET imaging (see [Section 9.1.9](#)).

If necessary, confirmatory imaging (for SoT) will be performed within 45 days following rhPSMA-7.3 (¹⁸F) PET imaging or attempted biopsy according to the algorithm in [Figure 3](#). If necessary, additional confirmatory imaging may be performed up to 90 days after rhPSMA-7.3 (¹⁸F) PET. Note: in patients with multiple PET-positive regions, confirmation of at least one PET-positive lesion in each region is required either by biopsy/surgical resection or confirmatory imaging. Patients may receive salvage treatment following further consultation with their physician (outside the scope of this study). The salvage treatment prescribed will be recorded. If treatment consists of a surgical resection, the histology obtained will be correlated with rhPSMA-7.3 (¹⁸F) PET imaging. Follow-up confirmatory imaging utilized as part of the SoT assessment should not delay the patient's treatment.

Note: due to the COVID-19 pandemic, biopsy and surgical procedures performed to obtain SoT histology and initial confirmatory imaging assessments (in patients not undergoing biopsy/resection) may be delayed up to Day 60 to ensure the safety (i.e., decreased potential exposure to severe acute respiratory syndrome coronavirus 2 [SARS-CoV-2]) of enrolled patients.

Safety (AEs and vital signs) will be monitored during the study.

An overview of the study is provided in the study schema ([Figure 1](#)).

4.2 Key Assumptions

Consistent with the data described in [Section 2](#), the detection rate of rhPSMA-7.3 (¹⁸F) PET in patients with a PSA level ≥ 1 ng/mL is expected to be at least 75%. The anticipated PPV in this population is expected to be approximately 80%. Therefore, the expected CDR in this subpopulation is $(75\% \times 80\%) = 60\%$.

However, in the subpopulation with a PSA level < 1 ng/mL, the detection rate is expected to be approximately 45%. The PPV is expected to be lower too (approximately 65%), since it will be more difficult to obtain proof of the lesions detected (as outlined in [Section 2](#)). Therefore, the CDR in this subpopulation is estimated to be low at $(45\% \times 65\%) = 29\%$.

It is planned to include approximately 40% of patients with a PSA level < 1 ng/mL and approximately 60% with a PSA level ≥ 1 ng/mL. Therefore, it is anticipated that the study will demonstrate an overall detection rate of approximately 60%, an overall PPV of at least 73.5% (taking into account multiple positive regions is anticipated in a proportion of patients), and, hence, an overall CDR of 49% (point estimates).

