	
Obuchowski, and McClish (2002), pg. 104) to adjust the variance estimates in the analysis based on clustering of regions within a patient. For the study to be considered a success, the p-values for both endpoints must be statistically significant for at least two out of the three readers (same readers for both CDR and PPV).
 
In the overall study population, the detection rate of rhPSMA-7.3 (¹⁸F) PET is expected to be approximately 60%, the overall PPV is estimated to be 73.5%, and the overall CDR is anticipated to be 49% (point estimates). The lower bound of the CI for the region level PPV will be set at 62.5% and the overall CDR will have a lower bound of 36.5%. The study will aim to include approximately 40% of patients with a PSA level <1 ng/mL and approximately 60% of patients with a PSA level \geq1 ng/mL.
 
Approximately 316 patients will be enrolled in this study. For the PPV endpoint, based on a one-sided 0.025 exact binomial test and assuming a true PPV of 73.5%, a sample size of 190 positive cases provides >88% power for the evaluation of region level PPV (H_0: PPV \leq62.5%). Assuming that 60% of all scans have a positive finding, a total of approximately 316 evaluable patients would be required to obtain 190 positive rhPSMA-7.3 (¹⁸F) PET cases. Note that PPV region-based analysis is expected to provide more than 88% power based upon the number of positive regions per patient being >1, even adjusting for the correlation between the regions within a patient. Thus, 316 patients are planned to be enrolled in order to get at least 190 cases with disease detected with rhPSMA-7.3 (¹⁸F) and an evaluable result.
 
For the patient level CDR endpoint, based on a one-sided 0.025 exact binomial test and assuming a true CDR of 49%, a sample size of 316 cases provides >99% power for the evaluation of CDR (H_0: CDR \leq36.5%).
 
Hence, a sample size of at least 316 patients is adequate based on the region level PPV endpoint and is expected to provide at least 90% power for the regional PPV analysis.
 
Dropouts who fail to complete all study procedures, for reasons other than due to adverse reactions/AEs deemed related to IP, will be withdrawn from the study and will be replaced. No more than 15% of patients enrolled will be replaced.
 
Secondary and exploratory endpoints will be summarized descriptively, with the exception of consistency of rhPSMA-7.3 (¹⁸F) scan interpretation by blinded independent readers which will be presented utilizing Kappa statistics. Two-sided 95% CIs will be presented, where applicable.

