16.8 Sample Size and Randomization

16.8.1 Assumptions

As discussed in [Section 4.2](#), in the overall study population, the detection rate of rhPSMA-7.3 (^{18}F) PET is expected to be approximately 60%, the overall PPV is estimated to be 73.5% and the overall CDR is anticipated to be 49% (point estimates). The lower bound of the CI for the region level PPV will be set at 62.5% and the overall CDR will have a lower bound of 36.5%. The study will aim to include approximately 40% of patients with a PSA level <1 ng/mL and approximately 60% of patients with a PSA level ≥ 1 ng/mL.

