16.8.2 Sample Size

Approximately 316 patients will be enrolled in this study. For the PPV endpoint, based on a one-sided 0.025 exact binomial test and assuming a true PPV of 73.5%, a sample size of 190 positive cases provides $>88\%$ power for the evaluation of region level PPV (H_0 : PPV $\leq 62.5\%$). Assuming that 60% of all scans have a positive finding, a total of approximately 316 evaluable patients would be required to obtain 190 positive rhPSMA-7.3 (^{18}F) PET cases. Note that the PPV region-based analysis is expected to provide more than 88% power based upon the number of positive regions per patient being >1 , even adjusting for the correlation between the regions within a patient. Thus, 316 patients are planned to be enrolled in order to get at least 190 cases with disease detected with rhPSMA-7.3 (^{18}F) and an evaluable result.

For the patient level CDR endpoint, based on a one-sided 0.025 exact binomial test and assuming a true CDR of 49%, a sample size of 316 cases provides $>99\%$ power for the evaluation of CDR (H_0 : CDR $\leq 36.5\%$).

Hence, a sample size of at least 316 patients is adequate based on the region level PPV endpoint and is expected to provide at least 90% power for the regional PPV analysis.

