2.3 Exploratory Objective(s)

The exploratory objectives of the study are to:

1. Assess the overall detection rate (without SoT confirmation) on a patient level and including detection rate subgroup analyses of patients: a) who have negative baseline conventional imaging, b) with reference standard histopathology available and unavailable, and detection rate stratified by PSA level and assessed by region.
2. Assess the patient level PPV in which a TP patient is defined as having at least one TP region, regardless of any coexisting FP regions.
3. Assess the impact of rhPSMA-7.3 (¹⁸F) PET on upstaging patients with BCR of PCa a) post-Radical prostatectomy (RP) or b) post-Radio therapy (RT) compared to conventional imaging.
4. Assess patient and regional level detection rates of rhPSMA-7.3 (¹⁸F) PET.
5. Assess patient and regional level detection rates of rhPSMA-7.3 (¹⁸F) PET as a function of PSA, prior Gleason score, and PSA doubling time (PSAdt) in a) post-RP or b) post-RT patients.

3 INVESTIGATIONAL PLAN**3.1 Overall Study Design and Plan**

This is a prospective, Phase 3, multicenter, single-arm, diagnostic imaging study designed to evaluate the safety and diagnostic performance of rh-PSMA7.3 (¹⁸F) PET ligand for imaging in men with suspected BCR of PCa based on elevated PSA following prior therapy.

Given the observed difference in performance of PSMA ligands in patients with PSA levels <1 ng/mL versus ≥1 ng/mL, the patient population will be weighted to prevent over-representation of patients with a PSA <1 ng/mL. The proportion of patients with a PSA <1 ng/mL will be capped at approximately 40% of total study population, which is consistent with the study population studied by [Fendler \(2019\)](#). Once 60% of the planned 190 positive cases have PSA level recorded in the eCRF, the proportion of included patients with a PSA <1 ng/mL will be assessed. If this proportion exceeds 60% then investigators will be told to stop further enrolment of this cohort.

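### The planned overall CDR of 49% and detection rate of about 60% do not follow from the stated strata and PSA mix, which give 47.7% and 63%; exact CDR power at 47.7% is 98.0%, not >99%

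*Protocol*

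**What the plan says.** Protocol 4.2, repeated in SAP 4.18.1, builds the planning values from two PSA strata:

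- PSA ≥1 ng/mL: detection at least 75%, PPV about 80%, CDR 75% × 80% = 60%.
- PSA <1 ng/mL: detection about 45%, PPV about 65%, CDR 45% × 65% = 29%.
- Planned mix: about 60% and 40% of patients respectively.

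From these it infers that "it is anticipated that the study will demonstrate an overall detection rate of approximately 60" per cent, with an overall PPV of at least 73.5%, "and, hence, an overall CDR of 49% (point estimates"). The synopsis and Protocol 16.8.1 repeat that "the overall CDR is anticipated to be 49% (point estimates").

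Protocol 16.8.2 and SAP 4.18.2 use both totals. The 49% gives the >99% power for CDR with 316 patients, tested against 36.5% by a one-sided 0.025 exact binomial test. The 60% converts 190 positive cases into patients: "Assuming that 60% of all scans have a positive finding, a total of approximately 316 evaluable patients would be required".

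Some inputs are worded as bounds. Protocol 2 says that "an estimated overall detection rate of ≥75% is reasonable for patients with a PSA level ≥1 ng/mL". The PSA <1 share "will be maximized at approximately 40" per cent in Protocol 4.1, and "will be capped at approximately 40% of total study population" in SAP 3.1.

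**The concern.** The text presents the overall figures as consequences of the strata and the mix, yet a reader who carries out the weighting gets neither. The printed CDR is 1.3 points too high and the printed detection rate 3 points too low, so one rounding or one shift in the mix cannot explain both.

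CDR is a co-primary endpoint, and 49% is the only basis for its stated power. If 49% cannot be reached from the inputs printed directly above it, the >99% statement has no support that a reader can trace.

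**Working it through.** **Inputs.** Strata and mix from Protocol 4.2 and SAP 4.18.1. Null value 36.5%, one-sided 0.025 exact binomial test and N=316 from Protocol 16.8.

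**1. The plan's own power figure.** The smallest r with P(X ≥ r | 316, 0.365) ≤ 0.025 is r = 133: P(X ≥ 133) = 0.0232 and P(X ≥ 132) = 0.0303. Power at a true CDR of 0.49 is P(X ≥ 133 | 316, 0.49) = 99.4%. The stated >99% therefore reproduces from 49%.

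**2. Overall values from the strata and mix.**

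- CDR = 0.6 × 0.75 × 0.80 + 0.4 × 0.45 × 0.65 = 0.360 + 0.117 = 47.7%. With the rounded 29% it is 0.360 + 0.116 = 47.6%.
- Detection = 0.6 × 0.75 + 0.4 × 0.45 = 0.450 + 0.180 = 63.0%.

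**3. Can another PSA mix give the printed pair?** Let s be the PSA <1 share.

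- CDR of 49%: s = (0.60 − 0.49)/(0.60 − 0.2925) = 35.8%, with detection 0.75 − 0.30 × 0.358 = 64.3%.
- Detection of 60%: s = (0.75 − 0.60)/0.30 = 50%, with CDR 0.5 × 0.60 + 0.5 × 0.2925 = 44.6%. This mix lies outside the plan's own cap of about 40%.

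More directly, 49%/60% = 81.7% confirmed among positive patients. With stratum CDRs formed as the plan forms them, that fraction is an average of 80% and 65% and cannot exceed 80%.

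**4. Do the inputs worded as bounds help?**

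- Raise PSA ≥1 detection alone: (0.49 − 0.117)/(0.6 × 0.80) = 77.7%, giving overall detection of 64.6%.
- Raise PSA <1 detection alone: (0.49 − 0.36)/(0.4 × 0.65) = 50%, giving overall detection of 65.0%.
- Hold detection at 63% and raise both PPVs by x: x = (0.49 − 0.477)/0.63 = 2.1 points, that is 82.1% and 67.1%. The plan states neither value.

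If detection is at least 75% and 45% and the PSA <1 share is at most 40%, overall detection cannot be below 63%.

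**5. Power at the recomputed CDR** (N=316, reject at ≥133):

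| True CDR | Basis | Exact power |
|---|---|---|
| 49.0% | printed | 99.4% |
| 48.9% | stated strata, s = 36% | 99.4% |
| 48.5% | stated strata, s = 37.5% | 99.0% |
| 47.7% | stated strata, s = 40% | 98.0% |
| 47.6% | as above, rounded 29% | 97.8% |

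**6. Effect on the PPV sample size.** 0.63 × 316 = 199 positive cases, against 0.60 × 316 = 190. For comparison, exact PPV power with 190 cases (62.5% against 73.5%, reject at ≥133) is 87.9%.

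**The case against.** **Patients with several positive regions.** PPV is a region-level measure, while CDR needs only one true-positive lesion in a patient, so patient-level CDR can exceed detection × region-level PPV. As an illustration, assume that a share m of positive patients has two regions, confirmed independently at the stratum PPVs. The plan prints no such share. The gain in CDR is m × (0.6 × 0.75 × 0.80 × 0.20 + 0.4 × 0.45 × 0.65 × 0.35) = 0.113m, which closes the 1.3-point gap at m of about 11.5%, or about 23% if the within-patient correlation is 0.5. This is a plausible route to 49%, but it is not the plan's route. Section 4.2 itself labels the stratum products as CDRs, and its remark about multiple regions qualifies the overall PPV. Nor does the mechanism explain 60% detection.

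**Hedged inputs.** Most inputs are approximate, PSA ≥1 detection is a minimum, and Protocol 2 also gives PSA <1 detection as ≥45%. On that reading 47.7% is close to the bottom of the plan's range. It stands that 49% is attainable, and that the 63% lower limit in step 4 depends on taking the floors and cap as firm. But higher detection rates or a lower PSA <1 share move overall detection further above 60%. Reading the approximations the other way lowers CDR: reaching 60% through PSA <1 detection alone needs (0.60 − 0.45)/0.4 = 37.5%, and CDR is then 0.36 + 0.4 × 0.375 × 0.65 = 45.8%.

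**Harmlessness.** The 60% figure is conservative for obtaining positive cases, the power statement is explicitly conditional on 49%, and no decision changes. All of this is true. It limits the importance of the point but does not make the derivation correct.

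**Conclusion.** The concern holds. On the stated strata and a 60/40 mix, the overall CDR is 47.7% and detection is 63%; the printed 49% and 60% follow neither separately nor together. The power calculation itself is sound; the unsupported element is its 49% input. At 47.7% the exact power is 98.0%, a loss of 1.4 points. Power of 99% needs a true CDR of about 48.5%, which with these strata means a PSA <1 share of 37.5% or less.

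The practical effect is small. CDR remains far better powered than PPV, and the extra positive cases at 63% detection favour PPV. The result takes the stratum values at their stated levels and the stratum CDRs as Section 4.2 defines them.

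**What to change.** In the protocol synopsis, Protocol 4.2 and 16.8, and SAP 4.18:

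1. Restate the overall CDR as about 47.7%, with about 98% power at N=316. Alternatively, keep 49% and print the inputs that yield it (the PSA <1 share, the stratum detection rates, or an explicit allowance for multi-region patients), and tie >99% to those inputs.
2. State overall detection as 63%, or say that 60% is a deliberately conservative figure for securing 190 positive cases.

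The cost is text edits only. Sample size, thresholds, analysis and decision rule stay as they are. The one drawback is a stated CDR power of about 98% in place of >99%, if the first option in item 1 is taken.
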